For symptomatic dermographism and cold urticaria, if the participant did experience symptoms from the provocation test that was incorrectly performed, the test can be repeated at a different area on the skin that has been 24 hours symptom free. There has to be a minimum of 30 minutes between provocation tests. For cholinergic urticaria, if the participant did experience symptoms from the provocation test that was incorrectly performed, the test can be repeated after all symptoms have subsided.

The results of the last repeat test are to be recorded in the eCRF.

The number of times the test is repeated is left to the discretion of the investigator, taking the participant's safety and well-being into consideration.

It should be noted, the provocation tests are considered to be completed correctly even if the test is stopped early due to participants reaching their maximum symptoms, results of which are to be recorded in the eCRF.

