### **Potential risks due to study procedures to study participants:**

- **Provocation tests**

The provocation tests used in the study (FricTest®4.0, TempTest®4.0 and pulse-controlled ergometry) are commonly used, are highly sensitive and specific for diagnosing and inducing symptoms associated with CINDU. Specific to cholinergic urticaria, the provocation test involves physical exercise to induce symptoms of CINDU. Since the ergometry is pulse-controlled, the provocation is gentle ([Altrichter et al 2014](#)). Mild increases in body temperature following physical exercise are likely. In the study by Altrichter et al, the maximum increase in body temperature from baseline noted in cholinergic urticaria patients was 2.52 °C versus 2.31 °C in healthy volunteers. The provocation test allows for recording of time to occurrence of hives. In the same study by Altrichter et al, the authors noted that while the median time to hives was 27 minutes, 19 minutes was the earliest time to occurrence of hives. The investigator will be instructed to keep patient safety as a priority and if participants experience uncontrolled hives or any discomfort within a short timeframe of initiation of provocation, the test may be stopped. Management of the reactions should be first considered, following with the administration of study treatment once the participants recover.

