#### **8.3.1.3 Pulse-controlled ergometry test**

To elicit symptoms of cholinergic urticaria in a clinical setting, pulse-controlled ergometry will be used. If a participant has risk factors for coronary artery disease, it is up to the discretion of the investigator to decide whether the patient needs cardiac clearance prior to undergoing the pulse controlled ergometry provocation test. In general, participants must be feeling well to perform this test. In this procedure, participants undergo pulse-controlled incremental ergometry for 30 min (stationary bicycle ride) increasing their pulse rate by 15 beats every 5 min to a final maximum increase of 90 beats per minute above the starting level at 30 min (Altrichter et al 2014). A pulse oximeter is fitted to the participant to monitor pulse rate. Only participants that are able to sweat should be included in the cholinergic urticaria cohort, hence, to detect sweating on day of randomization, starch-iodine powder or similar is applied to the lower back or other area that shows sweating. This sweat detection test must be performed on all provocation test days and is described in the provocation test manual for cholinergic urticaria.

The start time of sweating and the start time that hives appear are recorded on the eCRF. Time to appearance of hives correlates with disease activity; in other words, the sooner the hives appear, the more active the disease (Altrichter et al 2014). Observations are continued during a 10 min recovery period at the end of the 30 min of exercise.

Itchy hives are considered a positive response. Ten minutes after the end of the provocation test, the participant is asked to evaluate the severity of their itch, pain and burning using a 11 point numerical rating scale ranging from no symptom (scored 0) to worst possible symptom (scored 10). The investigator will also assess the severity of hives using the physician global assessment of severity of hives.

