#### 12.4.4 Handling of missing values not related to intercurrent event

If the provocation testing is stopped due to any reason e.g participant discomfort, technical issues the data will be considered as missing.

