## 12.5 Analysis supporting secondary objectives

For detailed definitions of secondary estimands, please refer to [Section 2.2](#). The following secondary endpoints will be assessed and included into the testing strategy for the three CINDU cohorts:

- **Symptomatic dermographism**
  1. proportion of participants achieving complete response in response to the FricTest 4.0 (Total Fric Score=0) at Week 12
  2. absolute change from baseline to Week 12 on itch NRS following the FricTest 4.0.
- **Cold urticaria**
  1. proportion of participants achieving complete response in response to the TempTest at Week 12
  2. change from baseline to Week 12 on itch NRS following the TempTest.
- **Cholinergic urticaria**
  1. proportion of participants achieving complete response in itch NRS following the pulse-controlled ergometry test, assessed as itch NRS=0 at Week 12.
  2. proportion of participants achieving complete response in physician global assessment (PGA) of severity of hives following the pulse-controlled ergometry test, assessed as PGA hive score=0 at Week 12.

The proportion of participants with complete response at Week 12 will be compared by the Fisher's Exact test between each of the ligelizumab dose group and the placebo group. In case of missing data caused by discontinuation due to reasons other than AE, lack of efficacy, or intake of prohibited medication, or missing data not related to intercurrent events, raw scores in corresponding provocation test (i.e. Total Fric Score, CTT, and itch NRS) will be first imputed as described in [Section 12.4.3](#) and [Section 12.4.4](#), respectively, then the missing responder status will be derived based on the imputed raw score. As sensitivity analysis, proportion of complete responders will be analyzed using a logistic regression model including treatment group, region/country and baseline score.

Change from baseline to Week 12 on itch NRS in response to provocation tests will be analyzed based on participants who have baseline scores greater than zero by two-sample t-test. In case of missing data caused by discontinuation due to reasons other than AE, lack of efficacy, or intake of prohibited medication, or missing data not related to intercurrent events, itch NRS will be imputed in a same manner as described in [Section 12.4.3](#) and [Section 12.4.4](#), respectively.

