2.5.3.2 Handling of missing values not related to intercurrent event

For each of the CINDU cohort, the following will be considered as intermittent missing data, which are not related to intercurrent event:

The provocation test is stopped due to any reason e.g. participant discomfort, technical issues the data will be considered as missing.

The provocation test is not performed due to any reasons other than specified intercurrent events

Symptomatic dermographism

Handling of missing or incomplete results in the FricTest 4.0:

The missing TFS will be multiply imputed under the MAR assumption for all the groups.

Cold urticaria

Handling of missing or incomplete results in response to the TempTest®:

The missing CTT will be multiply imputed under the MAR assumption for all the groups.

Cholinergic urticaria

Handling of missing or incomplete itch NRS results following the pulse-controlled ergometry test:

The missing itch NRS will be multiply imputed under the MAR assumption for both treatment groups.

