2.6.4 Handling of missing values not related to intercurrent event

For each of the CINDU cohort, the following will be considered as intermittent missing data, which are not related to intercurrent event:

- The provocation test is stopped due to any reason e.g. participant discomfort, technical issues the data will be considered as missing.
- The provocation test is not performed due to any reasons other than specified intercurrent events

Symptomatic dermographism

Handling of missing or incomplete results in the FricTest 4.0:

- The missing TFS=0 complete response status will be multiply imputed under the MAR assumption for all the groups.
- The missing itch NRS following the provocation test will be multiply imputed under the MAR assumption for all the groups.

Cold urticaria

Handling of missing or incomplete results in response to the TempTest®:

- The missing complete response status (a negative provocation test result for the lowest temperature (4°C) in TempTest®4.0) will be multiply imputed under the MAR assumption for all the groups.
- The missing itch NRS following the provocation test will be multiply imputed under the MAR assumption for all the groups.

Cholinergic urticaria

Handling of missing or incomplete results the following the pulse-controlled ergometry test:

- The missing itch NRS=0 complete response status will be multiply imputed under the MAR assumption for both treatment groups.

The missing PGA hive score=0 complete response status will be multiply imputed under the MAR assumption for both treatment groups.

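### Protocol 3.2 counts a provocation test stopped at maximum symptoms as completed and recorded, but protocol 12.4.4 and SAP 2.5.3.2 and 2.6.4 make any stopped test missing; the passages must be reconciled

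*Protocol*

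**What the plan says.** **Conduct text.** Protocol 3.2, after its rules on repeating a faulty test, notes that "the provocation tests are considered to be completed correctly even if the test is stopped early due to participants reaching their maximum symptoms". The same sentence requires the result to be entered in the eCRF. For ergometry, protocol 8.3.1.3 times the scoring from the end of the test, whenever that is: "Ten minutes after the end of the provocation test, the participant is asked to evaluate the severity of their itch, pain and burning". Protocol 4.5 adds, in its discussion of ergometry, that "if participants experience uncontrolled hives or any discomfort within a short timeframe of initiation of provocation, the test may be stopped".

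**Analysis text.** Protocol 12.4.4 says: "If the provocation testing is stopped due to any reason e.g participant discomfort, technical issues the data will be considered as missing". It then imputes Total Fric Score (TFS), critical temperature threshold (CTT) and itch NRS under MAR in every group. SAP 2.5.3.2 repeats the rule for the primary endpoint: "The provocation test is stopped due to any reason e.g. participant discomfort, technical issues the data will be considered as missing". SAP 2.6.4 repeats it for the secondary endpoints and, for the cholinergic cohort, adds: "The missing itch NRS=0 complete response status will be multiply imputed under the MAR assumption for both treatment groups". Protocol 12.5 imputes the raw score first, "then the missing responder status will be derived based on the imputed raw score". None of these sections mentions protocol 3.2 or exempts a stop at maximum symptoms.

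**The concern.** The same Week 12 test can be an observed severe result under protocol 3.2 and a missing value under protocol 12.4.4. A stop at maximum symptoms is caused by the outcome being measured, so for this subset missingness depends on the value itself and MAR is not credible. The value is also available, because it is scored after the test ends and must be recorded.

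The planned estimate of the primary treatment effect is at stake. So is the responder status of individuals: by either the SAP 2.6.4 or the protocol 12.5 route, a participant who reacted could be imputed as a complete responder.

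**Working it through.** **1. The passages side by side.**

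| | Protocol 3.2 | Protocol 12.4.4, SAP 2.5.3.2, SAP 2.6.4 |
|---|---|---|
| Test stopped at maximum symptoms | Completed correctly | Stopped, hence missing |
| Its result | Recorded in the eCRF | Replaced by MAR imputation |
| Exception or cross-reference | Not applicable | None |

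Participant discomfort is the first example of a stop in the analysis text. Protocol 4.5 names uncontrolled hives and discomfort together as grounds for stopping, so the two categories plausibly overlap.

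**2. Where it can occur.** The FricTest is a single stroke (protocol 8.3.1.1). The TempTest lasts up to about 5 minutes (8.3.1.2). Ergometry lasts 30 minutes (8.3.1.3) and is the only test for which protocol 4.5 discusses stopping. Exposure is therefore mainly the cholinergic cohort. No size was computed for TFS or CTT.

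**3. The plan's own figure.** Protocol 12.8.1, cholinergic: difference 1.65, SD 3.0, 79 per arm, 10% drop-out, one-sided 2.5%. Evaluable per arm: 79 × 0.9 ≈ 71. Standard error: 3.0 × √(2/71) = 0.504. Noncentrality: 1.65/0.504 = 3.28 on 140 df. Power is 90.2%, as stated. The stated power is not in dispute.

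**4. Illustration with assumed stop rates.** The model is:
- Baseline itch NRS: N(6, SD 2), rounded and limited to 1–10.
- Week 12 itch NRS: m + 0.5 × (baseline − 6) + 3.2z, rounded and limited to 0–10, with m = 5.4 on placebo and 3.47 on active. This gives a difference of about 1.65 and an SD of change of about 3.0.
- Week 8: same form, with residual correlation 0.7 to Week 12.
- Stops: only among Week 12 scores of 8 or more. The probability is 0.19 or 0.375 in both arms for the first two rows below, and set by arm for the third.
- Imputation: within arm, 20 imputations, Rubin's rules, one-sided 0.025, 71 per arm, 4,000 trials. The Monte Carlo standard error is 0.008 for the effect and about 0.5 points for power.

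| Stops, placebo/active | Full-data effect | Baseline only | Baseline + Week 8 | Shift | Power: full; baseline; + Week 8 |
|---|---|---|---|---|---|
| 5.1%/2.2% | 1.669 | 1.590 | 1.626 | −0.079; −0.043 | 90.6%; 87.4%; 89.0% |
| 9.9%/4.3% | 1.640 | 1.478 | 1.547 | −0.162; −0.093 | 89.2%; 82.5%; 85.9% |
| 5.1%/5.0% | 1.643 | 1.714 | 1.688 | +0.071; +0.045 | not tabulated |

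Allowing for variation between simulation runs, power in the second row is 82–84% from baseline only and 86–88% with Week 8. The baseline-only shift in the third row is +0.06 to +0.07. Equal rates are not neutral because the discarded high scores lie further from the active mean than from the placebo mean.

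With no treatment effect (m = 5.4 in both arms, stops 9.9%/9.8%), rejection is 2.9% from baseline only and 2.7% with Week 8, against 2.6% with full data. The Monte Carlo standard error is √(0.025 × 0.975/4000) ≈ 0.25 points.

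**5. A harsher version that can be checked by hand.** Take normal changes with SD 3 and means 0 and −1.65. Every value above a cut-off c goes missing, and nothing predicts it. The remaining mean is μ − σφ(a)/Φ(a), with a = (c − μ)/σ. If 10% of placebo tests stop, c = 3.84. Placebo: −3 × 0.1755/0.90 = −0.585. Active: a = 1.83, 3.3% stop, and the mean is −1.65 − 3 × 0.0746/0.9665 = −1.88. The difference is about 1.30, with power near 80%. At 5% placebo stops the figures are 1.43 and 85%.

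**The case against.** The best defence is that the specific rule governs the general one. Protocol 3.2 defines a stop at maximum symptoms as a completed test, and protocol 12.4.4 concerns missing or incomplete results, so such a test never reaches the missing-data rule. That reading is possible and is probably the intended one. But the analysis text does not state it. Its wording is unqualified, its first example overlaps with symptom stops, and someone programming from the SAP alone would set these values to missing.

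Other points stand in part:
- Discomfort on a bicycle need not be urticarial. Treating a stop for unrelated discomfort as missing conflicts with nothing in protocol 3.2.
- No stop rate is given. Protocol 4.5 cites a median of 27 minutes to hives and an earliest time of 19 minutes in a 30-minute test, which does not establish the rates assumed above.
- Protocol 12.4.5 allows tipping-point analyses to address uncertainty in the imputations. They were only to be done if needed, and SAP 2.5.4 now plans no sensitivity analyses.
- A score after a truncated ergometry follows less provocation than a full test, so analysing it as observed has a cost in comparability.

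A reader might also infer that the complete-response comparison would be badly distorted. The documents do not support that, and the model above cannot size it. It gives itch NRS=0 rates of about 7% and 19%, against the 13% and 38% assumed in protocol 12.8.2. What can be said is only that a participant who reacted could be imputed as a complete responder.

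**Conclusion.** The conflict is real and lies in the planned analysis: the missing-data rule, taken literally, discards recorded poor results that protocol 3.2 treats as valid. Size and direction depend on stop rates that the documents do not give. If symptom stops are more common on placebo, the planned cholinergic effect is pulled towards the null: about 0.08 (0.04 with Week 8) at 5%/2%, and 0.16 (0.09) at 10%/4%. At equal 5% rates it moves the other way by about 0.06 to 0.07 (0.04). These figures rest on the assumed score distribution, stop mechanism and imputation predictors.

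Two stronger readings are tempting. One is that the rule systematically favours one arm or inflates false positives. The direction is not fixed, and type I error was not materially changed in the null simulation. The other is that this trial's results are compromised. SAP 1, 2.6.2 and 4 cancel all efficacy testing, and SAP 1.1.2 reports that only 3 participants had completed the Week 12 visit, so no inference changes. At most, it is unclear how the Week 12 listings kept in SAP 2.5.2 would show such a value. Minor.

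**What to change.** Reconcile the passages. In protocol 12.4.4, SAP 2.5.3.2 and SAP 2.6.4, add one sentence: a test stopped early because the participant reached maximum symptoms, as described in protocol 3.2, counts as completed, and its recorded TFS, CTT, itch NRS or PGA hive score is analysed as observed. Derive complete response from that value by each endpoint's own definition: TFS=0, a negative test at 4°C, itch NRS=0, or PGA=0. Keep MAR imputation for tests not done, or stopped for technical or other reasons. In the listings still planned, show the recorded value with the reason for stopping.

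This changes only how data are handled, not when a test may be stopped. The cost is three sentences, since protocol 3.2 already requires the result to be recorded. There are two drawbacks. The stop reason must be identifiable in the data, and a score after a truncated test may be less comparable with one after a full test.

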##### Symptomatic dermographism

Handling of missing or incomplete results in the FricTest 4.0:

- The missing Total Fric Scores will be multiply imputed under the MAR assumption for all the groups.

##### Cold urticaria

Handling of missing or incomplete results in response to the TempTest®:

- The missing CTT will be multiply imputed under the MAR assumption for all the groups.

##### Cholinergic urticaria

Handling of missing or incomplete itch NRS results following the pulse-controlled ergometry test:

- The missing itch NRS will be multiply imputed under the MAR assumption for both treatment groups.

#### 12.4.5 Sensitivity analyses for primary endpoint/estimand

For all three CINDU cohorts, the following sensitivity analysis will be performed for the primary estimand, to assess the robustness of the estimation in the presence of deviations from the assumptions specified in the primary analysis.

- The ANCOVA (Analysis of covariance) model with treatment group, baseline scores, region/country as covariates will be performed. Intercurrent events will be handled in the same way as in the primary analysis.
- To account for uncertainty in the imputations, the tipping point analyses will be considered, if needed.

### 12.4.6 Supplementary analysis

In addition to the primary analysis, change from baseline at week 12 on Total Fric Score/CTT/itch NRS will be tested using Wilcoxon rank sum test for symptomatic dermographism, cold urticaria, and cholinergic urticaria respectively.

For each CINDU cohort, if the primary analysis is statistically significant, subgroup analyses to assess the homogeneity of the treatment effect across demographic and baseline disease characteristics may be performed.

Other supplementary analysis will be described in the SAP (Statistical Analysis Plan) as needed.

## 12.5 Analysis supporting secondary objectives

For detailed definitions of secondary estimands, please refer to [Section 2.2](#). The following secondary endpoints will be assessed and included into the testing strategy for the three CINDU cohorts:

- **Symptomatic dermographism**
  1. proportion of participants achieving complete response in response to the FricTest 4.0 (Total Fric Score=0) at Week 12
  2. absolute change from baseline to Week 12 on itch NRS following the FricTest 4.0.
- **Cold urticaria**
  1. proportion of participants achieving complete response in response to the TempTest at Week 12
  2. change from baseline to Week 12 on itch NRS following the TempTest.
- **Cholinergic urticaria**
  1. proportion of participants achieving complete response in itch NRS following the pulse-controlled ergometry test, assessed as itch NRS=0 at Week 12.
  2. proportion of participants achieving complete response in physician global assessment (PGA) of severity of hives following the pulse-controlled ergometry test, assessed as PGA hive score=0 at Week 12.

The proportion of participants with complete response at Week 12 will be compared by the Fisher's Exact test between each of the ligelizumab dose group and the placebo group. In case of missing data caused by discontinuation due to reasons other than AE, lack of efficacy, or intake of prohibited medication, or missing data not related to intercurrent events, raw scores in corresponding provocation test (i.e. Total Fric Score, CTT, and itch NRS) will be first imputed as described in [Section 12.4.3](#) and [Section 12.4.4](#), respectively, then the missing responder status will be derived based on the imputed raw score. As sensitivity analysis, proportion of complete responders will be analyzed using a logistic regression model including treatment group, region/country and baseline score.

Change from baseline to Week 12 on itch NRS in response to provocation tests will be analyzed based on participants who have baseline scores greater than zero by two-sample t-test. In case of missing data caused by discontinuation due to reasons other than AE, lack of efficacy, or intake of prohibited medication, or missing data not related to intercurrent events, itch NRS will be imputed in a same manner as described in [Section 12.4.3](#) and [Section 12.4.4](#), respectively.

## Testing strategy for symptomatic dermographism and cold urticaria

The following null hypotheses ( $H_0$ ) will be tested against the respective alternative hypotheses ( $H_A$ ) in a closed testing procedure (Bretz et al 2009), thus controlling the family-wise type I error which is set to 0.025 (one-sided) for each CINDU cohort.

### Primary endpoint

Total Fric Score/CTT change from baseline at Week 12

$H_{01}: \mu_{\text{igelizumab}} \geq \mu_{\text{Placebo}}$  versus  $H_{A1}: \mu_{\text{igelizumab}} < \mu_{\text{Placebo}}$

where  $\mu$  is the mean change from baseline in Total Fric Score/CTT at Week 12, as described in Section 2.1.

### Secondary endpoints

- proportion of participants achieving complete response in response to FricTest 4.0 and TempTest at Week 12

$H_{02}: \pi_{\text{igelizumab}} \leq \pi_{\text{Placebo}}$  versus  $H_{A2}: \pi_{\text{igelizumab}} > \pi_{\text{Placebo}}$

[figure not shown]
where  $\pi$  is the proportion of participants achieving complete response status at Week 12, as described in Section 2.2.

- itch NRS following provocation tests change from baseline at Week 12

$H_{03}: \mu_{\text{igelizumab}} \geq \mu_{\text{Placebo}}$  versus  $H_{A3}: \mu_{\text{igelizumab}} < \mu_{\text{Placebo}}$

where  $\mu$  is the mean change from baseline in itch NRS following the FricTest 4.0 and TempTest at Week 12, as described in Section 2.2.

